Only veterans will be enrolled in this study. Eligible subjects will be recruited from primary care and cardiology clinics at the MEDVAMC and will include patients in Stage A or B HF whose risk factors (which led to their classification as Stage A/B) are adequately controlled and who have an hs-cTnT level greater than 5 ng/L and estimated 10 year HF risk greater than 5%.

Eligible individuals will be randomized (equal numbers in each group) to spironolactone, carvedilol or usual care.

Randomization will be performed by the research pharmacy at MEDVAMC supported by the Institution For Clinical and Translational research (ICTR) at Baylor College of Medicine using deidentified data.

Subjects who qualify will have hs-cTnT measured using a novel high sensitivity assay along with NT-proBNP. Those with cTnT greater than 5 ng/L and an estimated 10-year HF risk greater than 5%, estimated based on a lab result based model will be eligible to continue in the study and will then have an echocardiogram, carotid ultrasound imaging, and arterial stiffness assessment (pulse wave velocity). The echocardiogram will be interpreted to ensure that there are no clinically significant abnormalities that should be addressed by the subjects physician or that would exclude the subject from the study.

The PI will review the images to ensure that they are of adequate quality to allow the measurement of cardiac strain (the primary end point). Those who meet all the inclusion criteria will then proceed to randomization.

RATIONALE FOR CHOICE OF STUDY POPULATION:

Our goal was to choose a population who were at higher risk among individuals with Stage A/B HF so that preventive therapies, if successful, would have a favorable risk vs. benefit ratio. Three important inclusion criteria were considered in the choice of our study population:

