Baseline labs including a comprehensive metabolic panel, lipid panel, and hemoglobin A1C will be assessed (unless labs within 3 months are available). Additional blood will be stored for future biomarker analysis. These blood samples will be stored in the Research commons freezer or the Winters Center freezers located in building 110 at the MEDVAMC. The biomarker analyses to be performed will be based on additional funding that will be obtained as the current grant that supports this study will not have adequate funds to run additional biomarkers. Hence while related to the study in that all the data from this study will be used, the funding is to be obtained in the future and the biomarkers to be decided in the future. Blood from only those who meet the troponin inclusion criteria and who are ultimately randomized to this study will be stored. The others will be discarded.

Randomization visit and titration of medications: After the pre-randomization visit, those individuals who meet the inclusion criteria including hs-cTnT levels, HF risk score will come for the randomization visit. A history (medical, surgical, social, family and medication history and review of systems) and physical examination will be performed, and the findings will be documented on the case report form. The physical examination

would include BP measurements (3 taken 2 minutes apart). Orthostatic BP measurements will be performed as well. We will use calibrated BP machines in the clinic for the purpose of the study. They will have a 2D and 3D echocardiogram with Doppler. Those with adequate images for cardiac strain assessment will then be randomized to one of the 3 groups. Randomization will be achieved with the help of the research pharmacy and ICTR (institute for clinical and translational research). Randomization will be stratified for age, presence of CHD, ACE-inhibitor/ARB use, and hs-cTnT levels greater than 14 ng/L. In addition to an echocardiogram, a carotid ultrasound and a pulse wave velocity assessment will be performed at the randomization visit

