Subjects randomized to the spironolactone group will be started at 25 mg daily, and titration up to 50 mg daily will be attempted (blood pressure, potassium levels permitting). Briefly, subjects will start taking their medication and 2 weeks later return for a brief visit when BP and potassium will be checked. If BP is greater than 125 mm Hg, spironolactone will be increased to 50 mg daily. Once maximum dose is achieved, serum potassium will be measured to ensure stability. For those randomized to spironolactone who have eGFR between 50 and 60 ml, medication will be started at 12.5 to 25 mg daily and then potassium, renal function measured at 2 weeks and 6 weeks and medication titrated based on results. In addition for those subjects with blood pressure on the lower side (120-130 mmHg systolic) or per principal investigators discretion spironolactone may be started at 12.5 mg daily for the first few days to ensure safety/ tolerability and then increased to 25 mg daily.

Subjects in the carvedilol group will similarly be started at 6.25 mg PO 2 times daily and titrated up to a maximum dose of 25 mg PO 2 times daily, again monitoring BP. Titration will be continued provided the systolic BP is >125 mm Hg. In addition for those subjects with blood pressure on the lower side (120-130 mmHg systolic) or per principal investigators discretion carvedilol may be started at 3.25 mg two times daily for the first few days to ensure safety/ tolerability and then increased to 6.25 mg two times daily.

Subjects in the usual-care group will continue receiving treatment from their primary care physician. However they will be required to come to the research clinics at baseline, 6 months, 12 months and at the end of study when history, physical, blood biomarker collection and imaging will be done similar to the carvedilol/ spironolactone treatment groups.

Visit 2: Subjects randomized to the spironolactone or carvedilol groups will come back for a 2-week visit, when they will have their BP checked and medications titrated if required. Those in the spironolactone arm will also have their serum potassium measured. As noted above for those on spironolactone and eGFR between 50-60 ml, potassium and renal function will be repeated at 6 weeks as well. Subjects may be called by the research coordinators approximately every 8 weeks for the first 6 months to enquire about tolerability and compliance. In addition this may help with subject retention.

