Visit 3: All subjects will return at 6 months. During the 6-month visit, all subjects will have a history and physical examination completed, and blood will be collected and part stored. Additionally, subjects will be interviewed about clinical events, including hospitalization, during the 6-month interval. Medication compliance will be assessed at this visit. Those on spironolactone will have their potassium checked

Visit 4: The 12 month visit will be identical to the 6 month visit

Visit 5: The final visit will capture details as in visit 3 and 4 but in addition also include all the imaging studies (echocardiogram, carotid ultrasound and pulse wave velocity measurement). Blood will be collected as well for biomarker assessment and additional samples stored for future research.

Subjects will be encouraged and requested to call/ notify us about any adverse events including side effects to medication, hospitalization, emergency room or urgent care visits. If there are any hospitalizations/ emergency room/ urgent care visits we will obtain information from the VA electronic medical record or from the hospital/ emergency room where they were cared for. There will be both paper and electronic data that will be nearly similar. The paper data will include the following HIPPA identifiers: name, date of birth, age, last four of the social security number, date of hospital admissions, date of discharge and any date of clinic visit during the duration of the study as well as participant address, phone number and email ID (if available). The electronic data stored at the VA will include name, last 4 of the social security number, date of birth, date of hospital admissions, date of discharge, any date of clinic visit and the research ID during the duration of the study. Electronic data stored in the BCM database which will be used for analysis will not have any HIPAA identifier and will include all other information. Data will be stored such that date of consent will be called "Day 0" and then other study events will be time stamped relative to the date of consent (example 6 month visit will be day 180 and so on). A date of birth will not be noted, but subject age will be recorded as this will be important in data analysis.

Sample Size/Data Analysis

Sample Size

How many subjects (or specimens, or charts) will be used in this study?

Local: 850 Worldwide: 850

Please indicate why you chose the sample size proposed:

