Data on change in strain with various medications are limited. However, a 1 to 1.5% absolute difference in longitudinal strain has been associated with outcomes. Therefore, assuming a conservative standard deviation of 3% (as described in studies), an alpha of 0.05, and a power of 0.8, we would require approximately 62 subjects per group.

Therefore, a sample size of 205-210 subjects should be a reasonable estimate (accounting for an approximately 10% drop-out rate)

Data Analysis

Provide a description of your plan for data analysis. State the types of comparisons you plan (e.g. comparison of means, comparison of proportions, regressions, analysis of variance).

Which is the PRIMARY comparison/analysis? How will the analyses proposed relate to the primary purposes of your study?

Primary analysis: To better inform the analyses planned, descriptive statistics (means and standard deviations of continuous variables and frequency of discrete variables) of subjects demographic characteristics and echocardiogram, vascular ultrasound, and biomarker variables will be computed at each measurement time and compared among the usual care and two drug treatment groups. All analyses will be conducted using the intention-to treat(ITT) principle. Statistical tests with a 2-sided P-value less than 0.05 will be considered statistically significant. When multiple comparisons are involved, Bonferroni correction for the type I error will be applied. Each continuous primary and secondary outcome will first be examined for its normality using the Shapiro Wilk test. When normality is verified, an analysis of variance (ANOVA) approach will be used to compare the mean change among the usual care and two drug treatment groups. Pairwise comparisons between the usual care and each of the drug groups will also be performed using the least significant difference method under the ANOVA framework. When the normality assumption is violated, the Kruskal Wallis nonparametric test will be applied.

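### Optional, low-cost gain: the primary ANOVA on change in strain is valid but leaves out baseline strain and the four stratification factors; a prespecified ANCOVA would usually be more precise

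*Combined protocol and SAP*

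**What the plan says.** The Design section identifies strain as the primary outcome; the echo images are checked for quality sufficient to "allow the measurement of cardiac strain (the primary end point"). Under Data Analysis, Primary analysis, once normality has been verified by Shapiro-Wilk, "an analysis of variance (ANOVA) approach will be used to compare the mean change among the usual care and two drug treatment groups". Drug-versus-usual-care comparisons "will also be performed using the least significant difference method under the ANOVA framework". Otherwise: "When the normality assumption is violated, the Kruskal Wallis nonparametric test will be applied". No baseline value or other covariate appears in any of these steps.

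The randomization-visit text under Procedure states: "Randomization will be stratified for age, presence of CHD, ACE-inhibitor/ARB use, and hs-cTnT levels greater than 14 ng/L". Baseline echocardiography is done at the same visit, before allocation. Covariate adjustment is mentioned only under Secondary Analysis, for a longitudinal model fitted with and without baseline covariates that are not listed.

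**The concern.** Analysing change amounts to fixing the regression slope of 18-month strain on baseline strain at 1. ANCOVA estimates that slope from the data. If the true slope is below 1, as regression to the mean usually makes it, the change score carries avoidable variance. Leaving out the stratification factors wastes any prognostic information they hold and tends to make the model-based standard errors slightly too large, so the test leans conservative.

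What is at stake is precision that needs no extra patients, visits or assays. It would be worth most if Bonferroni, which the plan promises for multiple comparisons, halves alpha for the two contrasts, or if the true difference lies near 1%, the lower end of the range quoted under Sample Size.

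There is also a small gap in the fallback. If normality is rejected, the only named test is a three-group one, which gives no estimate or confidence interval for each drug against usual care.

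**Working it through.** **Inputs from the documents.** Difference 1 to 1.5% absolute; SD 3%; two-sided alpha 0.05; power 0.8; 62 per group (Sample Size and Data Analysis). Three equal arms (Design). Four stratification factors (Procedure).

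**Assumed, because not given.** rho, the baseline to 18-month correlation, 0.3 to 0.9; k, the SD at 18 months divided by the SD at baseline, mainly 1.0; and that 3% is the SD of change.

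**1. The plan's own figure.** n = 2 × [3 × (1.960 + 0.842) / 1.5]² = 62.8 per group, which agrees with the stated 62. A difference of 1.0% would need 141.3, so the 62 rests on 1.5%. Power of the planned ANOVA at 62 per group (noncentral t, 186 − 3 = 183 df) is 0.79. At alpha 0.025 it is 0.70. For a 1.0% difference at alpha 0.05 it is 0.45.

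**2. Why ANCOVA gains.** Let b be the common slope, s² the residual variance and σ² the baseline variance. The per-arm variance is s² + (b − 1)²σ² for the change score and s² for ANCOVA. The excess is never negative and is zero only at b = 1. With b = rho × k, the ratio ANCOVA/change is k²(1 − rho²) / (1 + k² − 2·rho·k), which is (1 + rho)/2 at k = 1.

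**3. Cost of the covariates.** Baseline strain plus four factors is five slopes. The variance inflation is (183 − 1)/(183 − 5 − 1) = 182/177 = 1.028, or 2.8%, if the factors predict nothing. The four factors repay their own cost if together they explain 1 − 177/181 = 2.2% of residual variance.

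**4. Net results at k = 1** (62 per group, 178 df, SD of change 3%; residual SD = 3 × √net ratio):

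| rho | ratio | net ratio | net reduction | power, 1.5%, alpha 0.05 | power, 1.5%, alpha 0.025 | power, 1.0%, alpha 0.05 |
|---|---|---|---|---|---|---|
| planned ANOVA | 1 | 1 | – | 0.79 | 0.70 | 0.45 |
| 0.3 | 0.65 | 0.668 | 33% | 0.92 | 0.87 | 0.62 |
| 0.5 | 0.75 | 0.771 | 23% | 0.88 | 0.82 | 0.56 |
| 0.7 | 0.85 | 0.874 | 13% | 0.84 | 0.76 | 0.51 |
| 0.9 | 0.95 | 0.977 | 2% | 0.80 | 0.71 | 0.46 |

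A simulation with three arms of 62 and five covariates gave net ratios of 0.752 at rho 0.5 and 0.864 at rho 0.7, against 0.771 and 0.874 by formula. Differences of one or two percentage points should not be read closely.

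**5. Unequal SDs.** At k = 1.1 the net reductions at rho 0.3, 0.5, 0.7 and 0.9 are 27%, 16%, 5% and −3%. At k = 1.25 they are 19%, 8%, −1% and 2%, and −3% at rho 0.8. The worst net loss is the covariate cost, about 3%, where rho × k is 1.

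**6. If 3% is a single-visit SD** (k = 1). The SD of change is then 3√(2(1 − rho)) and the net ANCOVA SD is 3√((1 − rho²) × 1.028). Power for 1.5%, change against ANCOVA, is 0.65 against 0.82 at rho 0.3, 0.79 against 0.88 at 0.5, 0.95 against 0.97 at 0.7, and 1.00 against 1.00 at 0.9.

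**7. Unequal slopes.** Take illustrative slopes 0.95, 0.95 and 0.30, with baseline SD 3 and residual SD 2. One pooled slope is their mean, 0.733. For the first two arms the variance ratio is (4 + 0.217² × 9)/(4 + 0.05² × 9) = 4.42/4.02 = 1.10, a loss. Arm-specific slopes bring it to 0.99.

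**The case against.** The strongest reply is that nothing here is wrong. Under randomisation a change-score ANOVA is unbiased and widely accepted, and the stated sample size reproduces. That stands, and it is why the point is optional. A reader might infer that leaving out the stratification factors inflates false positives, or that the trial is underpowered. Neither follows: the omission tends to make the test conservative, and with 3% as the SD of change the planned analysis has 0.79 power for 1.5% at the sizing alpha.

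A second reply is that ANCOVA is not always better. This also stands in part. The tempting statement that it is never less precise needs a common slope, and step 7 shows a pooled slope losing about 10% for one contrast when slopes differ sharply. Conversely, the statement that nothing is gained at slope 1 applies to baseline strain only; the stratification factors can still help there.

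A third reply is that the Secondary Analysis model already allows baseline covariates. It is not the primary test. With imaging at baseline and the final visit only, complete data and covariates entered as main effects, its time-by-group term equals the change-score contrast and recovers none of this precision. With drop-out or more imaging visits it can recover some, and at high rho it could match ANCOVA. How much depends on correlations that the documents do not give.

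Finally, a reader might take the Kruskal-Wallis fallback as a threat to the primary result. Nothing in the documents suggests that strain is skewed; the gap matters mainly for biomarkers such as hs-cTnT and NT-proBNP.

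**Conclusion.** The point holds as an optional improvement in efficiency to a valid, unbiased primary analysis. With a common baseline slope, ANCOVA on baseline strain is asymptotically at least as precise as the change score and gains unless that slope is 1. With equal SDs and 3% as the SD of change, the net gain is material at rho 0.3 to 0.7 and negligible at 0.9. A loss of about 3% is possible at high rho or if the SD is larger at 18 months. The algebra is secure; the size of the gain is not, because rho, k and the meaning of the 3% SD are all assumptions.

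**What to change.** Before outcome data are seen, make the primary analysis an ANCOVA of 18-month strain on treatment group, baseline strain, age (continuous, or in the randomisation strata), CHD, ACE-inhibitor/ARB use and hs-cTnT above 14 ng/L. Take both drug-versus-usual-care contrasts, with confidence intervals, from that model. If baseline slopes may differ by arm, add a centred baseline-by-treatment term, or use arm-specific slopes with robust standard errors. Keep this model as primary whatever Shapiro-Wilk shows, with Kruskal-Wallis as a sensitivity analysis.

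The cost is analysis-plan wording and about five degrees of freedom: 2.8% in variance if the stratification factors are uninformative. Two interaction terms make it 182/175 = 1.040, or 4.0%. All covariates are already collected before randomisation.

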Purpose and Objectives

Our hypothesis is: In carefully selected subjects with Stage A or B HF (i.e., subjects with elevated cardiac troponin T (hs-cTnT) and elevated 10-year HF risk), augmented therapy for 18 months with the aldosterone antagonist spiroloactone or the nonselective beta-blocker carvedilol will decrease hs-cTnT and be associated with improved cardiac and vascular function compared with subjects treated with usual care.

Our specific aim is to evaluate using a prospective randomized open label blinded end point evaluation (PROBE) study if subjects with stage A or B HF (i.e., individuals at risk for incident HF hospitalization), increased hs-cTnT levels (>5

ng/L), 10-year estimated HF risk >5% and a systolic BP between 120 mmHg and 155 mmHg who receive aggressive treatment with the addition of spironolactone or carvedilol have decreases in hs-cTnT and improved noninvasive measures of cardiovascular function (cardiac and vascular strain) compared with usual care.

Protocol Risks/Subjects

Risk Category

Category 3: Research involving greater than minimal risk and no prospect of direct benefit to the individual subject, but likely to yield generalizable knowledge about the subject's disorder or condition.

Subjects

Gender:

Both

Age:

Adult (18-64 yrs), Geriatric (65+ yrs)

Ethnicity:

All Ethnicities

Primary Language:

English

Groups to be recruited will include:

Asymptomatic patients with chronic conditions, healthy

Which if any of the following vulnerable populations will be recruited as subjects?

Vulnerable populations require special protections. How will you obtain informed consent, protect subject confidentiality, and prevent undue coercion?

Pregnant woman/fetus

Will pregnant women and/or fetuses (as described in 45 CFR 46 Subpart B) be enrolled in the research?

No

Neonates

Will neonates of uncertain viability or nonviable neonates (as described in 45 CFR 46 Subpart B) be enrolled in the research?

No

Children

Will children be enrolled in the research?

No

Design/Procedure

Design

Select one category that most adequately describes your research:

u) Drug, Phase II, Single Center

Discuss the research design including but not limited to such issues as: probability of group assignment, potential for subject to be randomized to placebo group, use of control subjects, etc.

We will use a prospective open label blinded end point (PROBE) design to allow us to conduct our proposed study.

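### The plan promises Bonferroni but assigns the two drug-versus-usual-care contrasts to the unadjusted least significant difference method, with no divisor and no required F-test

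*Combined protocol and SAP*

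**What the plan says.** The hypothesis in Purpose and Objectives is that spironolactone or carvedilol "will decrease hs-cTnT and be associated with improved cardiac and vascular function compared with subjects treated with usual care". It is therefore answered by two contrasts, each drug against usual care. The Design section names cardiac strain as the primary end point.

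The Primary analysis paragraph of Data Analysis sets out, in this order:

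- A significance level: "Statistical tests with a 2-sided P-value less than 0.05 will be considered statistically significant".
- A general multiplicity rule: "When multiple comparisons are involved, Bonferroni correction for the type I error will be applied".
- A three-group ANOVA on mean change, used when normality is verified.
- The two contrasts of interest: "comparisons between the usual care and each of the drug groups will also be performed using the least significant difference method under the ANOVA framework".
- A fallback: "When the normality assumption is violated, the Kruskal Wallis nonparametric test will be applied". No pairwise test is named for this branch.

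The paragraph defines no family of tests, divisor or adjusted level. It does not make the pairwise tests depend on a significant F-test; they are simply done as well. The Secondary Analysis paragraph adds no multiplicity rule.

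The Sample Size section notes that "a 1 to 1.5% absolute difference in longitudinal strain has been associated with outcomes", takes an SD of 3%, and concludes that with "an alpha of 0.05, and a power of 0.8, we would require approximately 62 subjects per group". It does not say which difference, or which test, the calculation used.

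**The concern.** LSD, as a named procedure, judges each contrast at the unadjusted level. Naming it for these contrasts beside a Bonferroni commitment leaves three readings open:

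- (a) LSD at 0.05 for each contrast, unprotected.
- (b) The LSD statistic (pooled variance) judged at a Bonferroni threshold.
- (c) LSD only after a significant overall F-test.

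The reference to the ANOVA framework does not choose among them. It may mean only that the pooled variance is used.

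The choice bears on the trial's main claims, because an overall three-group test cannot say which drug differs from usual care. Reading (a) breaks the plan's own commitment to correction. Reading (b) keeps it, but the per-contrast comparison that best reproduces 62 per group then no longer has power 0.8. The readings can give different verdicts on the same data, and a rule left open can be settled after the results are seen.

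**Working it through.** **Inputs.** From the plan: three equal groups, 62 per group, SD 3 points, two-sided 0.05, power 0.8, strain as the single primary end point, two contrasts. Inferred: a difference of 1.5 points, the upper end of the plan's range.

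**Reproducing the plan's figure.** Normal formula: n per group = 2(z₀.₉₇₅ + z₀.₈)² SD²/δ².

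- δ = 1.5: 2 × (1.960 + 0.842)² × 9/2.25 = 62.8.
- δ = 1.0: 2 × (1.960 + 0.842)² × 9/1 = 141.3.

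So 62 fits 1.5 points at undivided 0.05. Dropout also fits: 186 × 1.10 = 205, 186/0.9 = 207 and (3 × 63)/0.9 = 210, against a stated 205-210.

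**Thresholds.** Pooled df = 3 × 62 − 3 = 183. SE of a contrast = 3√(2/62) = 0.539.

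- At 0.05: critical |t| 1.973, or 1.973 × 0.539 = 1.06 points.
- At 0.025: critical |t| 2.260, or 1.22 points.
- F-protected: critical F(2,183) = 3.045. With the third arm midway between the two compared, F = t²/2, so |t| must exceed √(2 × 3.045) = 2.468 (p = 0.0145, 1.33 points).

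**Error and power by rule.** Error rates are from 4 million simulated trials with no drug effect. Power is from the noncentral t distribution, or for F-protected LSD from 2 million simulated trials per setting.

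| Rule for the two contrasts | At least one false positive | Power per contrast, 1.5 points | Power per contrast, 1.0 point |
|---|---|---|---|
| (a) LSD at 0.05, unprotected | 9.1% | 0.791 | 0.455 |
| (b) Bonferroni at 0.025 | 4.6% | 0.700 | 0.345 |
| (c) F-protected LSD | 4.2% | 0.68-0.75 | 0.33-0.37 |
| Dunnett, for reference | 5.0% | 0.710 | 0.357 |

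A separate run of 400,000 trials gave 9.0% for (a), hence about 9%. The ranges for (c) hold while the other drug's effect lies between zero and that of the drug tested. At 1.5 points, power under (c) is about 0.79 if the other drug's effect is −0.75 or 2.5.

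The difference detectable with power 0.8 is 1.52 points at 0.05 and 1.67 points at 0.025.

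**How often the readings disagree**, for a drug with a true 1.5-point effect:

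- (a) versus (b): 0.791 − 0.700 = 0.091, about 9.1% of trials.
- (a) versus (c): 0.791 − 0.745 = 0.046 if the other drug's effect is 0 or 1.5, and 0.791 − 0.683 = 0.108 if it is 0.75. That is about 4.6% to 10.8%.
- (b) versus (c): 5.6% if the other drug's effect is 0.75 and 7.1% if it is 0 or 1.5. A contrast can pass either rule and fail the other.

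**What else the 0.8 might describe**, at 62 per group:

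- Overall F-test at 0.05: 0.82 if one or both drugs shift strain by 1.5 points (59 per group would give 0.80), but 0.70 if the other drug's effect is 0.75.
- At least one Bonferroni-significant contrast: 0.84 if both drugs shift strain by 1.5 points.

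**Kruskal-Wallis branch.** Pairwise rank tests over 60,000 null trials (normal; exponential data) gave at least one false positive in 9.1%; 9.0% at 0.05, 4.7%; 4.5% at 0.025, and 4.2%; 4.1% at 0.05 after a significant Kruskal-Wallis test.

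**The case against.** The best defence is that the paragraph can be harmonised. The Bonferroni sentence is general and precedes every named test, so LSD can supply the pooled-variance statistic and Bonferroni the threshold. The plan itself lists two contrasts and one primary end point, so a divisor of 2 follows although it is not printed. Alternatively, LSD can be taken to imply a preceding F-test, which with three groups holds the error below 5%. This is also a single-centre phase II trial with a surrogate end point, where correcting for two different drugs against one control is partly a matter of preference.

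Much of this stands, and it rules out three stronger readings that a reader might infer:

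- *The plan inflates type I error to 9%.* That happens under reading (a) only; (b) and (c) stay below 5%.
- *The stated power of 0.8 is wrong.* The documents do not say which test it refers to. The overall F-test, or the chance of at least one Bonferroni success, can reach 0.8 under the settings shown above. The two-group formula (62.8) fits 62 somewhat better than the ANOVA (59), but that is an inference.
- *hs-cTnT must be counted in the primary family.* It appears in the hypothesis, but the Design section gives the primary end point as cardiac strain.

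What the defence does not do is find a rule in the text. Each harmonising reading adds something unwritten: a threshold for LSD, or an F-test condition together with a waiver of Bonferroni. As for preference, the plan chose correction itself.

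**Conclusion.** The concern holds as an unresolved conflict in the primary inference. Bonferroni is promised, an unadjusted method is assigned to the two contrasts that answer the hypothesis, and nothing says which governs. Depending on the reading, the chance of at least one false positive on strain is about 9%, 4.6% or 4.2%, and per-contrast power at 1.5 points is 0.79, 0.70 or 0.68-0.75. If Bonferroni governs, each named contrast has power of about 0.70, not 0.8.

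These figures assume 62 evaluable per group, SD 3, strain as the only primary end point, two contrasts, and an inferred difference of 1.5 points. They do not show that error will be inflated or that the trial is too small; they show that the rule and the power target are undefined. This should be fixed before outcome data are compared, and it is not fatal to the design.

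**What to change.** In Primary analysis, name spironolactone versus usual care and carvedilol versus usual care, on change in cardiac strain, as the primary family. Replace the LSD wording with a statement that each contrast is tested at two-sided 0.025 (Bonferroni, two contrasts) using the ANOVA pooled variance. This is the smallest edit that keeps the plan's own commitment. Dunnett's test is acceptable, as is LSD only after a significant F-test if Bonferroni is expressly waived for these two contrasts.

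For the Kruskal-Wallis branch, name pairwise rank tests for the same two contrasts: at 0.025 each under Bonferroni or Dunnett, or at 0.05 only after a significant Kruskal-Wallis test under the F-protected rule.

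In Sample Size, state the difference used and which comparison the power refers to, then restate it. At 1.5 points, SD 3 and 62 per group, per-contrast power is about 0.70 (Bonferroni), 0.71 (Dunnett), or 0.68-0.75 (F-protected LSD, other drug's effect between 0 and 1.5 points).

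The cost is two or three sentences in the analysis section and one in the sample-size section. The downside is a less favourable stated power: under Bonferroni the difference detectable with power 0.8 becomes 1.67 rather than 1.52 points. No added enrolment is asked for. For information, keeping 0.8 per contrast at 1.5 points under Bonferroni would take 77 per group, or 3 × 77/0.9 = 257 with 10% dropout.
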